8.0 PHARMACEUTICAL INFORMATION

8.1 Doxorubicin (Adriamycin)

8.1.1 Doxorubicin Description

Doxorubicin is a cytotoxic anthracycline antibiotic isolated from cultures of *Streptomyces peucetius* var. *caesius*. Doxorubicin consists of a naphthacenequinone nucleus linked through a glycosidic bond at ring atom 7 to amino sugar, daunosamine. Chemically, doxorubicin hydrochloride is (8S,10S)-10-[(3-Amino-2,3,6-tideoxy- α -L-lyxo-hexopyranosyl)-oxy]-8-glycoloyl-7,8,9,10-tetrahydro-6,8,11-trihydroxy-1-methoxy-5,12-naphthacenedione hydrochloride.

Chemical name: C₂₇H₂₉NO₁₁•HCl
Molecular weight: 579.99

8.1.2 Clinical Pharmacology

The cytotoxic effect of doxorubicin on malignant cells and its toxic effects on various organs are thought to be related to nucleotide base intercalation and cell membrane lipid binding activities of doxorubicin. Intercalation inhibits nucleotide replication and action of DNA and RNA polymerases. The interaction of doxorubicin with topoisomerase II to form DNA-cleavable complexes appears to be an important mechanism of doxorubicin cytotoxic activity.

8.1.3 Pharmacokinetics and Drug Metabolism

Pharmacokinetic studies, determined in patients with various types of tumors undergoing either single or multi-agent therapy, have shown that doxorubicin follows a multiphasic disposition after intravenous injection. The initial distributive half-life of approximately 5 minutes suggests rapid tissue uptake of doxorubicin, while its slow elimination from tissues is reflected by a terminal half-life of 20 to 48 hours.

8.1.4 Supplier(s)

Doxorubicin is commercially available.

8.1.5 Dosage Form and Preparation

Doxorubicin for Injection is supplied as a sterile red-orange lyophilized powder in single dose flip-top vials in the following package strengths: 10 mg vial, 20 mg vial, 50 mg vial.

8.1.6 Storage and Stability

Store unconstituted vial at 20° to 25° C. Retain in carton until time of use. Discard unused portion.

After adding the diluent, the vial should be shaken and the contents allowed to dissolve. The reconstituted solution is stable for 7 days at room temperature and under normal room light and 15 days under refrigeration (2° to 8° C). It should be protected from exposure to sunlight.

8.1.7 Administration

When possible, to reduce the risk of developing cardiotoxicity in patients receiving doxorubicin after stopping treatment with other cardiotoxic agents, especially those with long half-lives such as trastuzumab, doxorubicin-based therapy should be delayed until the other agents have cleared from the circulation.

Care in the administration of doxorubicin will reduce the chance of perivenous infiltration. It may also decrease the chance of local reactions such as urticaria and erythematous streaking. On intravenous administration of doxorubicin, extravasation may occur with or without an accompanying burning or stinging sensation, even if blood returns well on aspiration of the infusion needle. If any signs or symptoms of extravasation have occurred, the injection or infusion should be immediately terminated and restarted in another vein.

Doxorubicin will be administered during this study at a dose of 25 mg/m² weekly for 6 weeks.

8.1.8 Special Handling Instructions

Caregivers should be counseled to take precautions (such as wearing latex gloves) to prevent contact with the patient's urine and other body fluids for at least 5 days after each treatment.

8.2 Etoposide (VP-16)

8.2.1 Clinical Pharmacology

A semisynthetic derivative of podophyllotoxin that forms a complex with topoisomerase II and DNA which results in single and double strand DNA breaks. Its main effect appears to be in the S and G2 phase of the cell cycle.

8.2.2 Pharmacokinetics and Drug Metabolism

The initial $t_{1/2}$ is 1.5 hours and the mean terminal half-life is 4 to 11 hours. It is primarily excreted in the urine. In children, approximately 55% of the dose is excreted in the urine as etoposide in 24 hours. The mean renal clearance of etoposide is 7 to 10 mL/min/m² or about 35% of the total body clearance over a dose range of 80 to 600 mg/m². Etoposide, therefore, is cleared by both renal and non renal processes, i.e., metabolism and biliary excretion. The effect of renal disease on plasma etoposide clearance is not known. Biliary excretion appears to be a minor route of etoposide elimination. Only 6% or less of an intravenous dose is recovered in the bile as etoposide. Metabolism accounts for most of the non renal clearance of etoposide. The maximum plasma concentration and area under the concentration time curve (AUC) exhibit a high degree of patient variability. Etoposide is highly bound to plasma proteins (~94%), primarily serum albumin. Pharmacodynamic studies have shown that etoposide systemic exposure is related to toxicity. Preliminary data suggests that systemic exposure for unbound etoposide correlates better than total (bound and unbound) etoposide. There is poor diffusion into the CSF < 5%. C_{max} and AUC values for orally administered etoposide capsules consistently fall in the same range as the C_{max} and AUC values for an intravenous dose of one-half the size of the oral dose. The overall mean value of oral capsule bioavailability is approximately 50% (range 25-75%).

8.2.3 Supplier(s)

Etoposide is commercially available.

8.2.4 Dosage Form and Preparation

Gelcaps: Etoposide is available as 50 mg pink capsules. Each liquid filled, soft gelatin capsule contains 50 mg of Etoposide in a vehicle consisting of citric acid, glycerin, purified water, and polyethylene glycol 400. The soft gelatin capsules

contain gelatin, glycerin, sorbitol, purified water, and parabens (ethyl and propyl) with the following dye system: iron oxide (red) and titanium dioxide; the capsules are printed with edible ink.

Injection for oral use: The Injection may be used orally for those children too young or unable to swallow capsules:

Etoposide for Injection is available in sterile multiple dose vials. The pH of the clear, nearly colorless to yellow liquid is 3 to 4. Each mL contains 20 mg etoposide, 2 mg citric acid, 30mg benzyl alcohol, 80 mg modified polysorbate 80/tween 80, 650 mg polyethylene glycol 300, and 30.5 percent (v/v) alcohol. Vial headspace contains nitrogen.

8.2.5 Storage and Stability

Etoposide capsules must be stored under refrigeration (2°-8°C or 36°- 46°F).The capsules are stable until the expiration date on the package.

Etoposide phosphate must be stored under refrigeration 2°-8°C (36°-46°F). Unopened vials of etoposide phosphate are stable until the expiration date on the package when stored at controlled room temperature (20°-25°C or 68°-77°F).

8.2.6 Administration

Gelcaps: Doses (up to 400 mg/day) can be given as a single once daily dose; doses >400 mg should be given in 2-4 divided doses. For the purposes of this protocol, dosing will be once daily as the 400 mg/day limit will not be exceeded.

Injection for oral use: For oral administration in children too young to take the capsules, the parenteral product can be used orally. A 1:1 dilution can be made by adding equal parts of normal saline and etoposide injection for a 10 mg/mL concentration which is stable for 22 days in Burrton plastic oral syringes (polypropylene) either exposed or protected from light (McLeod HL, Relling MV. Stability of etoposide solution for oral use. Am J Hosp Pharm. 1992;49;2784-5). This dilution can be administered directly to be followed by sour candy or gum, or can be further diluted immediately prior to administration with fruit juice. Etoposide injection can be mixed in orange juice, apple juice, or lemonade. Etoposide injection diluted this way in fruit juice must be consumed immediately as it tends to precipitate.

Undiluted etoposide injection (20 mg/mL) has been tested and is stable in a plastic syringe for 5 days when stored at room temperature under fluorescent light.

When etoposide is stored in plastic, there is potential for cracking of rigid plastic containers and of leaching of diethylhexyl phthalate (DEHP) from polyvinyl chloride (PVC) containers. Based on information provided by Bristol-Meyers Squibb Division of Oncology, undiluted etoposide appears to crack syringes made

of an acrylic-based plastic, polycarbonates, polyethylene glycol 300 or ABS (polymer produced by combining acrylonitrile, butadiene and styrene). Storing etoposide 10 mg/mL in polypropylene syringes should not pose a cracking risk or result in leaching of DEHP.

Concentrations need to be 0.4 mg/mL or less to substantially enhance taste. Etoposide stays in solution at 0.4 mg/mL for up to 3 hours in one of the above juices. If storage is required add 1 mL of undiluted etoposide injection (20 mg/mL) or 2 mL of the 10 mg/mL dilution above to 50 mL- of juice (1 & 2/3 ounces) for a concentration of 0.4 mg/ml, which is stable for up to 3 hours but should be consumed as soon as possible after mixing.

8.2.7 Special Handling Instructions

Use proper chemotherapy handling techniques.

9.0 CORRELATIVE STUDIES

9.1 DCE and DSC-MRI

All patients will undergo DSC and DCE-MRI at the following time points:

- no more than 3 weeks prior to MLA (OPTIONAL)
- within approximately 4 days after MLA
- 2-4 weeks (+/- 3 days) after MLA
- Every 12 weeks (+/- 7 days) following the last MRI for the first year or until disease progression for Arm A; every 8 weeks (+/- 7 days) until 2 years have elapsed or until disease progression, whichever comes first, for Arm B.

9.2 Blood for Correlative Studies

Patients will have 7 mL blood for serum drawn at the following time points:

- before MLA; this sample can be collected any time during the 3 day before or the day of the procedure until the start of the procedure
- within approximately 3 days after MLA
- weeks 2-4 post-MLA (Arm A only, at time of DSC/DCE-MRI)
- weekly (+/- 3 days) prior to (on the same day as) doxorubicin (Arm B only)
- Every 12 weeks (+/- 7 days) for the first year or until disease progression for Arm A; every 8 weeks (+/- 7 days) until 2 years have elapsed or disease progression, whichever comes first, for Arm B. Blood draws will be drawn one same days as MRIs, prior to scan.

A minimum of 2 ml will be drawn and placed in a red top tube and a minimum of 5 ml will be collected into a green top (heparin) tube. Specimens should be immediately transported to the Tissue Procurement Core (TPC) for processing.

9.3 Blood for Serum Biomarkers of BBB Disruption

For protein-based serum biomarker assays 0.5 to 1 ml serum will be to be aliquoted and stored at -80°C until used for ELISA analysis or for plasma microRNA-based assays in the [name] lab.

9.4 Blood for Phenotyping of Peripheral Blood Immune Cells

The remainder of serum will stored at -80°C until used for the Meso Scale Discovery (MSD)-based cytokine quantitation, which will be performed in the Immune Monitoring Core of the Center for Human Immunology and Immunotherapy Programs. Serum will be used in the MSD immunoassays to assess immunoregulatory cytokine and chemokine profiles pre- and post-treatment over time.

Blood obtained and stored for comparison of immune profiles of peripheral blood cells before and after MLA, provided there is no evidence of significant treatment-induced cytopenias. Blood will be Ficoll separated and the mononuclear cell population (PBMC) isolated per standard protocol through the TPC [59, 60]. The PBMC isolated from blood obtained prior to MLA will be cryopreserved for later analysis. The isolated monocytes will be incubated with IL-4 and GM-CSF to produce dendritic cells (DC)[60] which will then be cryopreserved for analysis of tumor-specific functional activity of peripheral blood immune cells detailed in section 9.4 below. To determine the phenotype of peripheral blood immune cells, following the 4-week interval, cryopreserved PBMC will be thawed and stained with labeled antibodies to CD4, CD8, CD45, CCR7, CD27, CD28, and CD62, as well as to markers of T cell hypofunctionality (PD-1, CTLA-4, LAG-3, TIM3, and ICOS). Specifically, we will compare levels of CD8⁺PD-1⁺LAG-3⁺ T cells between MLA-treated and untreated patients, as this cell population has been shown to mark tumor-specific CD8⁺ T cells. Cells will be assessed by flow cytometry in the CHiPs immune monitoring core.

Due to the limited blood volumes that may be available for some patients, our ability to conduct these cellular analyses may be limited. In this event, we will substitute quantitative PCR for lymphocyte cytokines—such as IFN- γ and TNF- α --from mRNA generated from PBMC to assess lymphocyte functional status.

9.5 OPTIONAL Biopsy for Tumor-Specific Functional Activity of Peripheral Blood Immune Cells

The patients in both arms may have a biopsy immediately before MLA. Specimens not used for histologic diagnosis will be cryopreserved in the tumor bank for later processing. Should our studies by either flow cytometry or qRT-PCR described in Section 9.4 show evidence of lymphocyte activation, then after PBMC samples have been obtained, we will test T cell reactivity in an in vitro stimulation assay. Dendritic cells matured from monocytes as described in Section 9.3 above will be incubated with freeze-thawed biopsy specimen lysate for 2 days and subsequently incubated with T cells purified from PBMC

using CD3/CD8-positive microbeads. Five days after stimulation, T cell reactivity will be assessed by ELISPOT assay for IFN- γ stimulation. This study will test whether MLA stimulates increased tumor-specific T cell recognition and activation. As in Section 9.4, the amount of blood drawn from some patients may be limited and could limit or ability to conduct these functional assays.

9.6 Quality of Life Assessments

Patients in both arms will undergo QOL assessments in the form of evaluation of Karnofsky/Lansky performance status at each physician visit and documented in the note.

10.0 STUDY CALENDAR

10.1 Arm A Study Calendar

	Baseline ¹	MLA	3 Days Post-MLA	2-4 Weeks Post-MLA	Every 12 Wks Thereafter for 12 months Post-MLA ⁴	F/U ¹⁰
Informed consent	X					
Medical history	X					
Physical exam incl. wt	X		X ³	X	X ⁹	X ¹¹
Karnofsky/Lansky	X		X	X	X ⁹	X ¹¹
CBC	X					
CMP	X					
Urine or serum β HCG	X ⁷					
MRI with DCE/DSC	X ⁸		X ²	X ²	X ⁹	X ¹¹
Biopsy		X ⁸				
Blood to measure brain-specific factors (Sections 9.2-9.4)	X		X ²	X ²	X ⁹	X ¹¹
Adverse event assessment ⁵		X	X	X	X	X

1. No more than 21 days prior to MLA.

2. +/- 3 days

3. Weight not required

4. Patients will be followed every 12 weeks from the Week 4 MRI until 1 year has elapsed since MLA or progression, whichever occurs first. After progression, vital status and subsequent treatment will be recorded.

5. Through one year or off protocol.

6. To be obtained with MRI.

7. Females of childbearing potential

8. Optional

9. +/- 7 days

10. F/U every 6 months or at event occurrence for 5 years or until death, whichever occurs first

11. +/- 2 weeks

10.2 Arm B Study Calendar

	B/L ¹	MLA	3 Days Post-MLA	Wk 1 ⁴	Wk 2 ⁴	Wk 3 ⁴	Wk 4 ⁴	Wk 5 ⁴	Wk 6 ⁴	Monthly ⁵	F/U ¹⁰
Informed consent	X										
Medical history	X									X	
Physical exam incl. wt	X			X	X	X	X	X	X	X	X ¹⁵
Karnofsky/Lansky	X			X	X	X	X	X	X	X	X ¹⁵
CBC	X			X	X	X	X	X	X	X	
CMP	X			X			X			X	
Urine or serum β HCG	X ¹²										
Echocardiogram	X ²										
MRI with DCE/DSC	X ¹⁴		X		X ¹¹					X ^{5,6}	
Biopsy		X ¹⁴									
Blood to measure brain-specific factors (Section 9.2-9.4)		X ³	X	X ⁷	X ⁷	X ⁷	X ⁷	X ⁷	X ⁷	X ^{5,6}	
Doxorubicin ⁸				X	X	X	X	X	X		
Etoposide ¹³										X	
AE assessment ⁹		X	-----								X

1. No more than 21 days prior to MLA.

2. No more than 1 year prior to registration.

3. May be collected any time during the 3 days before or the day of the procedure until the start of the procedure.

4. +/- 3 days

5. +/- 7 days

6. Every 8 weeks for the first 2 years or until disease progression, whichever occurs first. To coincide with MRI. After progression, vital status and subsequent treatment will be recorded.

7. Same day as chemotherapy.

8. To begin approximately 7 days after MLA.

9. Through one year or off protocol

10. Patients will be followed every 6 months or at event occurrence for 5 years or until death, whichever occurs first.

11. To be obtained 2-4 weeks post-MLA

12. Females of childbearing potential

13. To be started at time of count recovery after the 6 weeks of treatment with doxorubicin has concluded.

14. Optional

15. +/- 2 weeks

11.0 DATA SUBMISSION SCHEDULE

Case report forms with appropriate source documentation will be completed according to the schedule listed in this section.

Case Report Form	Submission Schedule
Original Consent Form	Prior to registration
On-Study Form	Prior to starting treatment
MLA Form	After procedure
Biopsy Form	After biopsy
QOL Form (documentation of performance status)	Weeks 1, 3, and 5 of doxorubicin With each cycle of etoposide Every 8 weeks for one year post-MLA
Doxorubicin Form (Arm B)	At the end of treatment with doxorubicin
Etoposide Form (Arm B)	At the end of each cycle of etoposide
Biomarkers Form	Refer to Section 9.2
Adverse Events Form	Continuous through 30 days after MLA (Arm A) Through 30 days after last dose of chemotherapy (Arm B)
Treatment Summary Form (Arm B)	Completion of treatment
Follow Up Form	Arm A: Every 12 weeks for one year post-MLA Arm B: Every 8 weeks for one year post-MLA
Tumor Response Form	With each MRI
AE Reporting Form	See Section 7.0 for reporting requirements

12.0 MEASUREMENT OF EFFECT

12.1 Antitumor Effect – Solid Tumors

For the purposes of this study, patients should be re-evaluated for response every 12 weeks on Arm A and every 8 weeks on Arm B. The DCE/DSC-MRI scan obtained within approximately 3 days after MLA will be used as the baseline scan for determining response. The DCE/DSC-MRI scans obtained at pre-MLA, post-MLA, and prior to 6 weeks post-MLA will not be assessed for disease response.

Response and progression will be evaluated in this study using the updated response assessment criteria for high-grade gliomas: Response Assessment in Neuro-Oncology (RANO) working group guideline [JCO 28(11): 1963-1972, 2010].

Criteria for Determining First Progression Depending on Time From Initial Chemoradiotherapy

First Progression	Definition
Progressive disease < 12 weeks after completion of chemoradiotherapy	
Progression can only be defined using diagnostic imaging if there is new enhancement outside of the radiation field (beyond the high-dose region or 80% isodose line) or if there is unequivocal evidence of viable tumor on histopathologic sampling (eg, solid tumor areas [ie, > 70% tumor cell nuclei in areas], high or progressive increase in MIB-1 proliferation index compared with prior biopsy, or evidence for histologic progression or increased anaplasia in tumor). Note: Given the difficulty of differentiating true progression from pseudoprogression, clinical decline alone, in the absence of radiographic or histologic confirmation of progression, will not be sufficient for definition of progressive disease in the first 12 weeks after completion of concurrent chemoradiotherapy.

Progressive disease ≥ 12 weeks after chemoradiotherapy completion	
 1. New contrast-enhancing lesion outside of radiation field on decreasing, stable, or increasing doses of corticosteroids. 2. Increase by ≥ 25% in the sum of the products of perpendicular diameters between the first postradiotherapy scan, or a subsequent scan with smaller tumor size, and the scan at 12 weeks or later on stable or increasing doses of corticosteroids. 3. Clinical deterioration not attributable to concurrent medication or comorbid conditions is sufficient to declare progression on current treatment but not for entry onto a clinical trial for recurrence. 4. For patients receiving antiangiogenic therapy, significant increase in T2/FLAIR nonenhancing lesion may also be considered progressive disease. The increased T2/FLAIR must have occurred with the patient on stable or increasing doses of corticosteroids compared with baseline scan or best response after initiation of therapy and not be a result of comorbid events (eg, effects of radiation therapy, demyelination, ischemic injury, infection, seizures, postoperative changes, or other treatment effects).

Criteria for Response Assessment Incorporating MRI and Clinical Factors (Adapted from JCO 2010)

Response	Criteria
Complete response	
 • Requires all of the following: complete disappearance of all enhancing measurable and nonmeasurable disease sustained for at least 4 weeks. • No new lesions; stable or improved nonenhancing (T2/FLAIR) lesions. • Patients must be off corticosteroids (or on physiologic replacement doses only) and stable or improved clinically. Note: Patients with nonmeasurable disease only cannot have a complete response; the best response possible is stable disease.

	
radiation therapy, demyelination, ischemic injury, infection, seizures, postoperative changes, or other treatment effects).
 
 • Any new measurable lesion within the 3 cm radius of the rim of the MLA-treated recurrent tumor. ‡ • Clear clinical deterioration not attributable to other causes apart from the tumor (e.g. seizures, medication adverse effects, complications of therapy, cerebrovascular events, infection, and so on) or changes in corticosteroid dose. • Failure to return for evaluation as a result of death or deteriorating condition; or clear progression of nonmeasurable disease.

- NOTE. All measurable and nonmeasurable lesions must be assessed using the same techniques as at baseline.
- Abbreviations: MRI, magnetic resonance imaging; FLAIR, fluid-attenuated inversion recovery.
- * Stable doses of corticosteroids include patients not on corticosteroids.
- ‡ If any new measurable lesion is outside the 3 cm radius of the rim of the MLA-treated recurrent tumor or is located in the contralateral hemisphere regardless of its distance from the rim of the MLA-treated tumor AND there is not any measurable lesion within the 3 cm radius, the patient will be considered to have progressive disease but will not be considered evaluable for PFS in this study, in which only local disease control or failure is measured.

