12.2 Disease Parameters

Measurable disease: Bi-dimensionally measurable lesions with clearly defined margins by MRI scan. All tumor measurements must be recorded in millimeters (or decimal fractions of centimeters).

Non-measurable disease: Uni-dimensionally measurable lesions or lesions with margins not clearly defined such as areas of T2/FLAIR signal abnormality or poorly defined enhancing abnormality.

Note: For cystic lesions, the only measurable part is any enhancement area around the cyst that is clearly defined and bi-dimensionally measurable. The cyst itself should not be considered measurable or non-measurable disease.

Target lesions: All measurable lesions that are residual of the lesion treated with MLA or that are located within the 3 cm radius of the rim of the MLA-treated recurrent tumor should be identified as target lesions and recorded and measured. Target lesions should be selected on the basis of their size (lesions with the longest diameter), but in addition should be those that lend themselves to reproducible repeated measurements. It may be the case that, on occasion, the largest lesion does not lend itself to reproducible measurement in which circumstance the next largest lesion, which can be measured reproducibly should be selected. When there are too many measurable lesions, choose the largest 3 lesions as target lesions to follow. The other measurable lesions should be considered evaluable for

the purpose of objective status determination.

Non-target lesions: All non-measurable lesions should be identified as non-target lesions and should also be recorded at baseline. Measurements of these lesions are not required, but the presence, absence, or in rare cases unequivocal progression of each should be noted throughout follow-up.

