12.3.2 Evaluation of Non-Target Lesions

Complete Response (CR): Disappearance of all non-target lesions.

Non-CR/Non-PD: Persistence of one or more non-target lesion(s).

Progressive Disease (PD): Appearance of one or more new lesions and/or unequivocal progression of existing non-target lesions on stable or increasing doses of corticosteroids compared with baseline scan or best response after initiation of therapy* not caused by comorbid events (e.g. radiation therapy, demyelination, ischemic injury, infection, seizures, postoperative changes, or other treatment effects). Unequivocal progression should not normally trump target lesion status. It must be representative of overall disease status change, not a single lesion increase.

Although a clear progression of “non-target” lesions only is exceptional, the opinion of the treating physician should prevail in such circumstances, and the progression status should be confirmed at a later time by the review panel (or Principal Investigator).

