12.3.3 Evaluation of Best Overall Response

The best overall response is the best response recorded from the start of the treatment until disease progression/recurrence (taking as reference for progressive disease the smallest measurements recorded since the treatment started). The patient's best response assignment will depend on the achievement of both measurement and confirmation criteria.

Summary of the RANO Response Criteria (Adapted from JCO 2010)

Criterion	CR	PR	SD	PD
T1 gadolinium enhancing disease	None	≥ 50% ↓	< 50% ↓ but < 25% ↑	≥ 25% ↑*
T2/FLAIR	Stable or ↓	Stable or ↓	Stable or ↓	↑*
New lesion	None	None	None	Present*
Corticosteroids	None	Stable or ↓	Stable or ↓	NA†
Clinical status	Stable or ↑	Stable or ↑	Stable or ↑	↓*
Requirement for response	All	All	All	Any*

Abbreviations: RANO, Response Assessment in Neuro-Oncology; CR, complete response; PR, partial response; SD, stable disease; PD, progressive disease; FLAIR, fluid-attenuated inversion recovery; NA, not applicable.

* Progression occurs when this criterion is present.

† Increase in corticosteroids alone will not be taken into account in determining progression in the absence of persistent clinical deterioration.

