12.3.6 Progression-Free Survival

PFS is defined as the duration of time from start of treatment to time of progression or death, whichever occurs first.

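### Section 12.1, footnote ‡, classes distant-only new disease as progression but takes the patient out of PFS, so the Arm B 6-month PFS has no single definition

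*Combined protocol and SAP*

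**What the plan says.** Footnote ‡ belongs to the new-lesion item in the Progression row of the Section 12.1 response table. That item reads "Any new measurable lesion within the 3 cm radius of the rim of the MLA-treated recurrent tumor". The footnote covers a new measurable lesion beyond that radius, or in the contralateral hemisphere, with a second condition: "AND there is not any measurable lesion within the 3 cm radius". When both conditions are met, "the patient will be considered to have progressive disease but will not be considered evaluable for PFS in this study". The reason given is that this is a study "in which only local disease control or failure is measured".

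Other sections bear on the same event:

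- Section 12.3.6: "PFS is defined as the duration of time from start of treatment to time of progression or death, whichever occurs first". It has no local limit and no exclusion.
- Section 2.1 makes 6-month PFS the Arm B primary objective, with no restriction by site.
- Section 12.2 includes among target lesions "All measurable lesions that are residual of the lesion treated with MLA or that are located within the 3 cm radius" of the treated rim.
- Section 12.3.2 defines non-target progression as "Appearance of one or more new lesions and/or unequivocal progression of existing non-target lesions", with no distance limit. In the Section 12.3.3 summary table a new lesion falls in the PD column, with the note "Progression occurs when this criterion is present".
- Section 14 plans Kaplan-Meier estimates of PFS, relates the permeability score to 6-month PFS, and fits a Cox model for PFS. It has no rule for patients the footnote removes.

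**The concern.** One event is called progression and is then kept out of the endpoint that measures progression. An analyst following Section 12.3.6 counts a failure. One following the footnote removes the patient, and Section 14 does not say whether that means deletion or censoring. Nor does the footnote say what happens to a later death, which Section 12.3.6 treats as an event.

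Removal depends on what happened after treatment, so the analysis set is selected on outcome. If the distant progression falls within six months, the patient removed is a failure of the primary objective. The same quantity is reused for the permeability score and the Cox model, and Section 14 says the data will be used to design later studies.

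**Working it through.** **Inputs.** Six patients in Arm B (Sections 5.1.2 and 14). The plan states no target rate, alpha or power for 6-month PFS, so there is no figure to reproduce. The event counts and distant shares below are assumptions, except where a source is given.

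**1. Can the passages be read together?**

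| Patient at the scan | Section 12.1 row and footnote ‡ | Sections 12.3.2 and 12.3.3 | Section 12.3.6 |
|---|---|---|---|
| New distant lesion, nothing measurable within 3 cm | Progression, but removed from PFS | Progression | PFS event |
| New distant lesion plus a measurable residual at the treated site | Neither the row's new-lesion item nor the footnote applies as worded | Progression | PFS event, if it is progression |

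In the first line the conflict is direct: the footnote itself calls the event progression, and Section 12.3.6 makes progression an event. In the second line the answer depends on whether the local residual is measurable, and on whether the footnote's second condition is meant to cover only new lesions. It does not say so.

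**2. Would a local-control endpoint remove these patients?** No. The footnote applies only when nothing measurable lies within 3 cm. On measurable disease, these patients are locally controlled up to that scan and contribute follow-up to that date.

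**3. Effect of one distant-only failure by month 6, with k of 6 progression-free.**

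- Counted as an event: k/6. Excluded: k/5. The difference is k/5 − k/6 = k/30.
- k = 3: 3/6 = 50.0% (exact 95% CI 11.8-88.2) against 3/5 = 60.0% (14.7-94.7).
- Across k: no change at k = 0, 3.3 points at k = 1, 16.7 points at k = 5 (5/6 = 83.3% against 5/5 = 100%).
- Two such failures with k = 3: 3/6 = 50.0% against 3/4 = 75.0%.

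**4. Censored instead.** Three progression-free, two local failures and one distant-only failure, Kaplan-Meier at month 6:

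- distant first: 4/5 × 3/4 = 0.600
- distant between the local failures: 5/6 × 3/4 = 0.625
- distant last: 5/6 × 4/5 = 0.667
- counted as an event, in any order: 5/6 × 4/5 × 3/4 = 0.500

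**5. Expected shift.** Let p be the true 6-month PFS and d the share of progressions by month 6 that meet the footnote's condition. Excluding only those early failures gives p / [1 − (1 − p)d]. With p = 0.30 assumed, d = 0.10, 0.20 and 0.30 give 0.323, 0.349 and 0.380. The only related figure in the plan is one glioblastoma series in Section 1.2, with 90% of relapses within 2-3 cm. That suggests d near 0.10, but Arm B takes any relapsed malignant type. For scale, the exact 95% CI for 2/6 is 4.3-77.7%.

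**6. How often would it matter?** If four of six progress, the chance that at least one meets the condition is 1 − (1 − d)^4: 34.4%, 59.0% and 76.0% for the same three values of d.

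**The case against.** The strongest reply is that the rule is deliberate. The footnote states its purpose, Section 1.5 frames Arm B around peritumoral control, and Section 12.2 ties the target lesions to the treated region. The footnote could be a study-specific exception to a general definition. There is also a practical reason: protocol MRI stops at progression (Section 9.1), after which vital status and subsequent treatment are followed (Section 5.9), so later local status is not observed by protocol. This stands as an explanation of intent. It supports ending local follow-up at that scan, by censoring or as a competing event. It does not support deleting the patient, and the exception never reaches Sections 2.1, 12.3.6 or 14.

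Three stronger readings are tempting, and the documents do not support them:

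- **A clear contradiction with Section 5.5.** That section makes Arm B patients with at least two doxorubicin doses evaluable for efficacy. Efficacy is wider than PFS, so a patient could be evaluable for response or survival and not for PFS. The conflict is partial at most.
- **A large or known bias.** The expected shifts are small and rest on assumed rates. The direction is upward if only failures by month 6 are removed. If a distant progression after month 6 also removed the patient retrospectively, 3/6 would become 2/5 (40%). That is one possible reading, and the footnote does not say it.
- **That the broader new-lesion rule is the right one.** The sections differ, and nothing in them settles which should prevail.

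**Conclusion.** The point holds at moderate severity. Footnote ‡ contradicts Section 12.3.6 and the Section 2.1 objective, and Section 14 leaves the handling open. Two analysts with the same six patients could report 50%, 60%, 62.5% or 66.7% for one early distant-only failure and three patients progression-free. The figure obtained by removal is neither PFS as defined nor local control.

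The size depends on assumed event counts and on a distant share that the plan does not give for this population. Any shift is small beside the sampling error of six patients, and no test or threshold depends on 6-month PFS. The defect is that a primary objective has no single definition.

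**What to change.** **(a) Analysis of distant-only progression.** In footnote ‡ and Section 14, keep these patients in PFS and 6-month PFS and count the distant progression as an event on the date of that scan, in line with Section 12.3.6. Add a listing of the site of first failure, within or beyond 3 cm. That keeps the local-control question visible. If the sponsor wants local control as the endpoint instead, name it so in Sections 2.1, 12.3.6 and 14, keep all patients, and treat distant-only progression and death as competing events.

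**(b) Progression wording.** The 3 cm limit in the Progression row and the footnote's second condition must be reconciled with Sections 12.3.2 and 12.3.3, notably for a patient with a measurable local residual and a new distant lesion. This review does not choose the progression rule, because documented progression also governs stopping of treatment (Section 5.8).

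**Cost.** Option (a) needs a change to the footnote, a sentence in Section 14 and one listing; the alternative needs renaming in three sections. Neither needs new data. The 6-month PFS figure may be slightly less favourable.
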